### **9.3.5 Evaluation of Exploratory Parameters**

Changes from baseline in PD parameters will be computed, as appropriate. All exploratory parameters will be summarized using descriptive statistics. Graphs of change from baseline will be presented, as appropriate.

### **9.3.6 Evaluation of Pharmacokinetic Parameters**

PK parameters will be computed, as appropriate, from the individual serum concentrations using a non-compartmental approach. All PK parameters will be summarized using descriptive statistics: N, mean, SD, min, max, median, CV %, and GM and GM CV%. Serum concentrations of PRA023 will be summarized.

### **9.3.7 Evaluation of Safety Parameters**

No formal statistical evaluation will be applied to the safety and tolerability variables. However, a clinical interpretation will be made based on the side effect profile to judge the safety of PRA023.

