## 2 STUDY OBJECTIVES

### 2.1 Primary Objective

- To assess the safety and tolerability of PRA023 following 12-weeks of induction therapy
- To compare the efficacy of PRA023 vs placebo for induction of clinical remission at Week 12

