#### 3.1 Primary Objective Evaluation

- The proportion of subjects reporting adverse events (AEs), serious adverse events (SAEs), AEs leading to discontinuation, and markedly abnormal laboratory values.
- The proportion of subjects in the 3-component Modified Mayo Score clinical remission (as defined by endoscopic subscore of 0 or 1, rectal bleeding subscore of 0, and stool frequency subscore of 0 or 1 and not greater than Baseline) at Week 12. The 3-component Modified Mayo Score ranges from 0-9 and includes rectal bleeding, stool frequency and endoscopic assessment domains.

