### 8.3 Evaluation of Safety Variables

Data will be summarized with respect to safety observations. Monitoring of AEs, physical examinations, vital signs, ECGs, safety and tolerability monitoring evaluations, clinical laboratory evaluations, and special procedures are detailed in [Section 6.3](#).

All available safety data for all randomized subjects who receive at least one dose of PRA023 will be included in the safety analysis, which will be primarily descriptive.

The safety variables will be:

- Hematology, chemistry, coagulation, and urinalysis
- Vital signs
- ECG parameters

- Physical examination
- AEs and SAEs
  - AEs of special interest: infections, acute infusion reaction (within 1 hour of completion of infusion), and peri-infusion reaction (within 24 hours of completion of infusion)
  - AEs in subjects who are ADA positive

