### 9.3.2 Evaluation of Efficacy Parameters

The efficacy assessment will test for the difference between PRA023 and placebo groups in FAS.

The primary endpoint will be analyzed and compared between PRA023 and placebo treatment groups in FAS from Cohort 1. The primary endpoint, the proportion of subjects achieving clinical remission, will be tested between the 2 treatment groups at 1-sided significance level of 0.025 using CMH with stratification factors at randomization. If significant, the 1st secondary endpoint of proportion of subjects achieving endoscopic improvement will be tested between the 2 treatment groups at 1-sided significance level of 0.025. If significant, the 2nd, 3rd, 4th, and 5th secondary endpoints will be tested sequentially, each at 1-sided significance level of 0.025. Testing for statistical significance will stop when the first endpoint is not statistically significant at level of 0.025 and all remaining p values will be nominal.

Treatment difference for primary and secondary endpoints for Cohort 1 will be estimated along with 95% CI for all subjects in FAS. The secondary endpoints in CDx+ subjects will be summarized and compared between PRA023 and placebo groups in FAS for CDx+, while the treatment difference will be estimated with 95% CI. Additional efficacy analysis will be detailed in SAP.

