#### **9.3.7.1 Adverse Events and Adverse Events of Special Interest**

All AEs will be coded using most current version of Medical Dictionary for Regulatory Activities (MedDRA). All reported adverse events will be assigned to the SOC and PT according to MedDRA. The number and percentage of subjects reporting adverse events (all, serious, related) will be tabulated by overall and treatment. AEs will be summarized by SOC and PT. AEs will also be summarized by relationship to the study drug, seriousness and severity.

A treatment-emergent AE (TEAE) will be defined as an AE that began or worsened on or after the first treatment dose. AEs recorded prior to the first infusion of study treatment will be considered non-treatment-emergent.

All reported AEs (treatment-emergent or not) will be listed. Only TEAEs will be summarized.

AEs of special interest including infections, acute infusion reaction (within 1 hour of completion of infusion), and peri-infusion reaction (within 24 hours of completion of infusion) will be summarized based on a pre-specified MedDRA list.

AEs occurring in subjects who are considered immunogenicity positive will also be summarized.

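### The safety proportions are a primary endpoint, but the protocol plans them as counts and percentages by arm, with no between-arm difference or interval to show what excess remains unexcluded

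*Protocol*

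**What the plan says.** Protocol Section 2.1 lists two primary objectives. The first is "To assess the safety and tolerability of PRA023 following 12-weeks of induction therapy"; the second is "To compare the efficacy of PRA023 vs placebo for induction of clinical remission at Week 12". Section 3.1 gives the safety endpoint as "The proportion of subjects reporting adverse events (AEs), serious adverse events (SAEs), AEs leading to discontinuation, and markedly abnormal laboratory values".

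Section 9.3.7 sets the analysis rule: "No formal statistical evaluation will be applied to the safety and tolerability variables". Safety is judged in another way: "a clinical interpretation will be made based on the side effect profile to judge the safety of PRA023". Section 8.3 describes the data that "will be included in the safety analysis, which will be primarily descriptive".

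For adverse events, Section 9.3.7.1 says "The number and percentage of subjects reporting adverse events (all, serious, related) will be tabulated by overall and treatment". It adds summaries by system organ class and preferred term, relationship, seriousness and severity, and for events of special interest. Section 9.3.7.3 plans laboratory and vital-sign changes by treatment and a laboratory shift table. None of these sections names a between-arm difference or a confidence interval.

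Section 9.3.2, on efficacy, does commit to intervals: "Treatment difference for primary and secondary endpoints for Cohort 1 will be estimated along with 95% CI for all subjects in FAS".

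The SAP supplied is an addendum. Its introduction limits it to the multiplicity approach and an added CDx+ interim analysis; it says nothing on safety.

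**The concern.** The randomised placebo arm allows a direct estimate of how much PRA023 changes each safety proportion. With 60 subjects per arm in Cohort 1, or about 84 per arm once Cohort 2 is added, two similar percentages for an uncommon event are easily read as the absence of a signal, even when the data remain compatible with a material excess. A percentage alone does not show how large that remaining excess could be. Because the proportions are a primary endpoint, the report should say what the trial has and has not excluded, as it will for remission.

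**Working it through.** **Inputs.** 60 per arm in Cohort 1 (Protocol 8.2). Cohort 2 size 48 (SAP addendum 3.1), so (120 + 48)/2 = 84 per arm with 1:1 allocation (Protocol 8.1). The documents give no adverse event or SAE rates, so every event rate below is an assumption, shown over a range.

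**The plan's own figure.** The protocol states no size, power or precision for safety. Its only power statement for a primary endpoint is above 80% for remission, 5% v 24%, 60 per arm, one-sided 0.025. With the pooled-variance normal approximation:

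- Power = Φ{[d√n − 1.96√(2p̄(1 − p̄))] / √(p₁(1 − p₁) + p₂(1 − p₂))}
- d = 0.19, p̄ = 0.145: (1.472 − 0.976)/0.479 = 1.034, so power = 84.9%. The stated figure reproduces.
- The same formula for an SAE rate doubling from 5% to 10% gives 18% at 60 per arm and 23% at 84. A significance test would therefore be uninformative for uncommon events, which supports leaving tests out.

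**What equal observed proportions leave open.** Newcombe interval, with Wilson limits l and u for each arm. When both arms show the same proportion p, the half-width is √[(p − l)² + (u − p)²].

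- 3/60 in each arm: p = 5.00%, l = 1.71%, u = 13.70%; √(3.29² + 8.70²) = 9.3 points.
- 4/84 in each arm: p = 4.76%, l = 1.87%, u = 11.61%; √(2.89² + 6.85²) = 7.4 points.

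| Same count in each arm | 95% CI for the difference (points) |
|---|---|
| 1/60 | ±7.3 |
| 3/60 | ±9.3 |
| 6/60 | ±11.5 |
| 12/60 | ±14.3 |
| 4/84 | ±7.4 |
| 8/84 | ±9.4 |

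With no events in an arm, the upper limit of the exact two-sided 95% interval for the true rate is 1 − 0.025^(1/n): 6.0% for n = 60 and 4.3% for n = 84.

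**How often a true doubling would not show in the counts.** P(X on PRA023 ≤ X on placebo) = Σₖ P(X placebo = k) · P(X PRA023 ≤ k), with independent binomials. Ties are included.

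| True SAE rate, placebo to PRA023 | 60 per arm | 84 per arm |
|---|---|---|
| 2% to 4% | 36% | 30% |
| 5% to 10% | 19% | 14% |
| 10% to 20% | 8% | 4% |

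For 5% to 10% at 60 per arm, the 19.0% consists of 8.2% exact ties and 10.8% with strictly fewer events on PRA023.

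**Whether the planned tables contain the endpoint.** Setting Section 3.1 beside Sections 9.3.7.1 and 9.3.7.3:

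- Adverse events and SAEs: number and percentage by treatment are planned.
- Adverse events leading to discontinuation: not among the categories that 9.3.7.1 names.
- Markedly abnormal laboratory values: 9.3.7.3 plans changes and out-of-range shifts. No threshold for markedly abnormal, and no tabulation of that proportion, appears in these documents.
- Comparator: Section 8.3 takes randomised subjects with at least one dose of PRA023, while Section 9.1.1 takes those with at least one dose of study drug. Read literally, 8.3 leaves out placebo subjects who never go on to PRA023 in the open-label extension.

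**The case against.** The strongest case on the other side is that the plan is coherent as it stands. The safety objective is to assess and the efficacy objective is to compare. No safety hypothesis, margin or sample size is stated, and descriptive safety is a reasonable choice for a proof-of-concept study. That stands, and no test is asked for here.

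Three stronger readings are tempting, and the documents do not support them.

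- A reader might infer that 9.3.7 forbids any statistics on safety. It excludes formal evaluation. A descriptive interval is not clearly prohibited.
- A reader might infer that the interval commitment in 9.3.2 covers safety, so that 9.3.7 contradicts it. That sentence sits under the efficacy heading and applies to the full analysis set, and the section uses the primary endpoint to mean clinical remission. It shows that the two primary endpoints are handled differently, not that the protocol contradicts itself.
- A reader might infer that safety will be judged from bare percentages. Severity, relationship, special-interest events, laboratory shifts and periodic data monitoring committee review are all planned. None of them, however, gives the uncertainty of the difference in the four named proportions.

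Two further points limit the finding. SAP V01 of 10 August 2022 is not among the documents and may already contain these intervals. Also, a reader given counts and denominators can compute an interval, and printing it does not make it narrower. That second point holds only for proportions that are tabulated, and two of the four have no named table here.

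**Conclusion.** The point holds as a gap in precision. The protocol makes safety proportions a primary endpoint and states no between-arm difference or interval for them. Under the assumed counts, equal SAE proportions near 5% would leave an excess of about 9 points unexcluded in Cohort 1 and about 7 points with both cohorts. Under the assumed doublings, PRA023 would show no more events than placebo in 8% to 36% of trials at 60 per arm and 4% to 30% at 84. These figures depend on event rates that the documents do not give.

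The finding does not make the descriptive approach wrong and does not touch the efficacy analysis. It is a worthwhile, low-cost improvement, subject to what SAP V01 already contains.

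**What to change.** Reword the first sentence of Section 9.3.7 along these lines: *No hypothesis tests will be done on safety variables. For each primary safety proportion, the PRA023-placebo risk difference with an unadjusted 95% CI (Newcombe) will be given for the 12-week blinded induction period, in all treated subjects and in Cohort 1.* If SAP V01 already provides this, align 9.3.7 with it.

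In the same edit:

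- add adverse events leading to discontinuation to the tabulations in 9.3.7.1;
- define the markedly abnormal laboratory proportion and tabulate it by treatment;
- reconcile Section 8.3 with Section 9.1.1 so that the full placebo comparator is included.

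The remaining safety tables stay descriptive. The cost is a few table rows, one laboratory definition and one population correction. The downside is a set of intervals without multiplicity adjustment, which a footnote should state.

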#### **9.3.7.1 Adverse Events and Adverse Events of Special Interest**

All AEs will be coded using most current version of Medical Dictionary for Regulatory Activities (MedDRA). All reported adverse events will be assigned to the SOC and PT according to MedDRA. The number and percentage of subjects reporting adverse events (all, serious, related) will be tabulated by overall and treatment. AEs will be summarized by SOC and PT. AEs will also be summarized by relationship to the study drug, seriousness and severity.

A treatment-emergent AE (TEAE) will be defined as an AE that began or worsened on or after the first treatment dose. AEs recorded prior to the first infusion of study treatment will be considered non-treatment-emergent.

All reported AEs (treatment-emergent or not) will be listed. Only TEAEs will be summarized.

AEs of special interest including infections, acute infusion reaction (within 1 hour of completion of infusion), and peri-infusion reaction (within 24 hours of completion of infusion) will be summarized based on a pre-specified MedDRA list.

AEs occurring in subjects who are considered immunogenicity positive will also be summarized.

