--	--

	
For subjects assigned to the 100 mg Q4W OLE arm, the dose may be escalated to 250 mg Q4W if disease activity is not adequately controlled in the Investigator's opinion.
 
The study is being amended by the Sponsor to extend the OLE period beyond 132/134 weeks to Week 168/170 based on emerging safety data in both this study as well as a concurrent open-label Phase 2 study in Crohn's disease. This extension is to obtain safety data for at least 2 years' of PRA023 drug exposure for at least 100 subjects in this study, assuming 20% annual dropout rate. The OLE period may be further extended beyond 168/170 weeks based on emerging safety data in a future amendment.
 
The study also includes an optional PK sub-study during the IP for subjects who consent to additional PK sampling.

SAMPLE SIZE:	
The study is planned to randomize up to approximately 170 subjects, approximately 120 in Cohort 1 and up to 50 in Cohort 2. A sample size of 60 per arm in Cohort 1 will enable a statistical power of > 80% for the primary endpoint at 1-sided significance level of 0.025 using Cochran-Mantel-Haenszel (CMH), assuming clinical remission rate of 5% for placebo and 24% for PRA023. Additionally, the sample size will confer > 80% power to achieve statistical significance for the 1st secondary endpoint of endoscopic improvement with an overall 1-sided alpha level of 0.025, assuming the endoscopic improvement rates are 15% and 38% for placebo and PRA023 groups, respectively.
 
Additionally, for analyses of the CDx population (combining CDx+ subjects from Cohort 1 and Cohort 2), a sample size of 40 per arm will provide a statistical power of <math>\geq 80\%</math> at a 1-sided alpha level of 0.025, according to a group sequential design with a non-binding futility interim analysis when approximately 18 subjects per arm are anticipated to reach Week 12, assuming clinical remission rate of 5% for placebo and 31% for PRA023.

SUBJECT TYPE:	Male or female subjects $\geq 18$ years of age with moderately to severely active UC.
FORMULATIONS:	PRA023 will be supplied in 10 mL vials each containing 500 mg PRA023 (60 mg/mL concentrate for solution for infusion) for IV administration after reconstitution.

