### 9.3.4 Evaluation of Immunogenicity

The proportion of samples positive for ADA and the proportion of subjects with any sample positive for ADA will be summarized by dose using descriptive statistics. The PK parameters of all subjects and subjects with no sample positive for ADA will be summarized to assess whether ADA has an impact on PK.

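### The AE summary for ADA-positive subjects has no ADA-negative comparator and no exposure adjustment, so it cannot show whether ADA is linked to AEs

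*Protocol*

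**What the plan says.** The supplied plan for relating ADA to safety is one sentence in Protocol Section 9.3.7.1, "AEs occurring in subjects who are considered immunogenicity positive will also be summarized", and a matching item in the safety variables of Section 8.3, "AEs in subjects who are ADA positive".

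The surrounding text gives the context:

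- **Comparator.** The other AE tables "will be tabulated by overall and treatment", as numbers and percentages of subjects, not by ADA status. For PK, by contrast, Section 9.3.4 names a negative group: "The PK parameters of all subjects and subjects with no sample positive for ADA will be summarized".
- **Definition of positive.** Neither sentence defines it. The nearest wording is the ADA incidence summary in Section 9.3.4: "the proportion of subjects with any sample positive for ADA will be summarized by dose using descriptive statistics". It is not tied to the AE summary.
- **Time window.** The only AE window is the general one: "A treatment-emergent AE (TEAE) will be defined as an AE that began or worsened on or after the first treatment dose".
- **Status of the analysis.** Section 9.3.7 states: "No formal statistical evaluation will be applied to the safety and tolerability variables". Safety is judged by clinical interpretation.

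The supplied SAP document is an addendum to SAP V01. It covers multiplicity and the CDx analyses and does not mention ADA.

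**The concern.** Protocol Section 5.4 lists anaphylaxis, cytokine release syndrome, infusion reactions and delayed hypersensitivity among the major safety concerns associated with immunogenicity. Section 1.3.2 attributes findings in the 6-week monkey study, including one death, to ADA and immune complexes, although these did not recur in the 6-month study. Whether ADA-positive subjects have more such reactions is therefore a natural question for the safety report.

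A table of positive subjects alone contains no contrast, so it cannot answer that question. Readers will probably look for a contrast in the overall or by-treatment tables. In the extension, which runs to Week 168/170, follow-up varies widely. A subject who stays longer has more time to develop ADA and more time to report an AE. Crude percentages could then differ with no effect of ADA.

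**Working it through.** The documents give no figure for this summary, so there is none to reproduce. The check asks how large a difference in crude percentages could arise when ADA has no effect.

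**Inputs from the documents.** Dropout is 20% per year (Synopsis: "assuming 20% annual dropout rate"). Treatment runs to Week 170 for responders, plus 12 weeks of follow-up. ADA sampling approximates Tables 2, 3 and 5: during induction, at Weeks 26, 42 and 50, about every 6 months after that, at early termination, and 4, 8 and 12 weeks after dosing.

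**Assumed inputs.** ADA incidence is 5%, 20% or 50%, and AE incidence 10%, 30% or 60%. These are annual for the long run and by Week 12 for the induction run. Hazards are constant, all subjects are at risk of ADA from Week 0, ADA and AEs are independent, and AEs do not cause dropout. Positive means any positive sample.

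**Formula.** Weekly hazard = −ln(1 − p)/52 (or /12 for induction). Each of 400,000 simulated subjects has exponential times to dropout, ADA and first AE.

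**Check on follow-up.** The dropout hazard is −ln(0.8)/52 = 0.00429 per week. Mean treatment time is (1 − e^(−0.00429×170))/0.00429 = 120.7 weeks, so mean follow-up is 120.7 + 12 = 132.7 weeks. In the simulation with ADA at 20% per year, 0.415 × 155.4 + 0.585 × 116.6 = 132.7 weeks, which agrees.

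**To Week 170 plus 12 weeks, ADA developing throughout**

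| ADA/yr | AE/yr | Ever positive | AE, positive | AE, never positive | Difference (points) |
|---|---|---|---|---|---|
| 5% | 10% | 12.1% | 27.0% | 22.4% | 4.6 |
| 5% | 30% | 12.2% | 64.4% | 54.8% | 9.6 |
| 5% | 60% | 12.1% | 90.7% | 81.4% | 9.3 |
| 20% | 10% | 41.5% | 26.6% | 20.5% | 6.2 |
| 20% | 30% | 41.6% | 63.6% | 50.7% | 12.8 |
| 20% | 60% | 41.6% | 90.2% | 77.1% | 13.1 |
| 50% | 10% | 75.9% | 25.6% | 14.6% | 11.0 |
| 50% | 30% | 75.9% | 61.6% | 38.5% | 23.1 |
| 50% | 60% | 75.9% | 88.3% | 64.3% | 24.0 |

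Differences are taken before rounding. Mean follow-up is 149 to 158 weeks in ever-positive and 81 to 129 weeks in never-positive subjects.

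**Against an all-subjects column.** That column includes the positives, so the excess is (1 − share positive) × difference. With ADA 20% and AE 30% it is 0.584 × 12.8 = 7.5 points. Over the nine rows it runs from 0.241 × 11.0 = 2.7 to 0.878 × 9.6 = 8.4 points.

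**ADA only in the first 12 weeks (20% of subjects).** AE percentages, positive against negative, are 22.7 vs 23.0, 56.2 vs 56.2 and 82.9 vs 82.6. All are within about 0.3 points.

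**Induction only.** Mean time on study is 11.9 weeks against 11.5 to 11.7. Differences run from −0.2 to +1.7 points.

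**Rates per person-time.** The ratio of ever-positive to never-positive is 0.99 to 1.02 in the nine long-run and nine induction scenarios.

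**Timing.** In the long run, 41% to 74% of first AEs in ever-positive subjects come before the first positive sample, with no ADA effect at all.

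**The case against.** Three readings stronger than the text allows are tempting.

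- A reader might infer that the plan counts ever-positive subjects and includes events before the first positive sample. Section 9.3.7.1 says neither. Both are inferences, from the ADA incidence wording in Section 9.3.4 and from the general treatment-emergent definition.
- A reader might infer that the table will show a spurious association. A positive-only table shows no association; someone has to supply the contrast from elsewhere.
- A reader might take an infection rate of 0.5 per year (assumed) and set 1 − e^(−0.5×12/52) = 11% against 1 − e^(−0.5×3.5) = 83%. That compares 12 weeks with 3.5 years of follow-up, not ADA-positive with ADA-negative subjects.

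Further points on the other side stand. The Protocol leaves detail to the SAP, and SAP V01 may already define this table. The analysis is descriptive, and all AEs are listed. Subjects who leave early still give ADA samples at early termination and after dosing; the simulation includes these in the long run. The bias is negligible over induction, the period of the primary safety objective.

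There is also a fair objection to a strict time-dependent remedy. After Week 12, responders are sampled for ADA at Weeks 26, 42 and 50 and then every 6 months. A reaction caused by ADA that arose between samples would be counted as ADA-negative, which biases towards no effect.

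None of this supplies a comparator or an exposure adjustment in the supplied text.

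**Conclusion.** The point holds in a limited form. As supplied, the plan describes AEs in ADA-positive subjects with no ADA-negative group and no adjustment for exposure, so the table cannot inform the concerns in Section 5.4. If it is read against other crude percentages in the extension, time on study could produce a difference with no true effect. That difference is about 5 to 24 points against never-positive subjects, or about 3 to 8 against all subjects, if ADA keeps developing. It is about 0 if ADA develops early, and at most 1.7 points over induction.

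These sizes rest on assumed ADA and AE rates, constant hazards, the any-sample definition and AEs that do not drive dropout. The documents give no ADA incidence, so which case applies is unknown. This is a cheap improvement to a descriptive summary and does not touch the primary or key secondary analyses.

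**What to change.** Unless SAP V01 already does this, in which case a cross-reference is enough:

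1. State how ADA-positive status is defined for this summary.
2. Among PRA023-exposed subjects, tabulate treatment-emergent AEs and AEs of special interest for ADA-positive and ADA-negative subjects side by side. Give counts with percentages and rates per 100 patient-years on PRA023.
3. Show induction separately from the extension. Person-time rates remove the artefact when hazards are constant. If AEs cluster early, a pooled rate would favour the longer-followed group.
4. List infusion and hypersensitivity reactions with onset relative to the last negative and first confirmed positive ADA sample. Do not reclassify all earlier events as ADA-negative.

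The cost is one extra table and one listing, from event and sample dates that should already be in the database. Counts will be small and intervals wide, and seroconversion will be dated only to within the sampling interval.
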